7.1. Discontinuation of Study Intervention

In some instances, it may be necessary for a participant to permanently discontinue study intervention. See Section 8.3 for safety assessments.

7.2. Participant Discontinuation/Withdrawal from the Study

If study intervention is permanently discontinued, the participant will still be invited to the 12month visit.

If the participant withdraws consent for disclosure of future information, the sponsor may retain and continue to use any data collected before such a withdrawal of consent.

The participant may request destruction of any samples taken and not tested, and the investigator must document this in the site study records.

7.3. Lost to Follow-up

Not applicable. Examination at 18 months is voluntary. Missing data due to lost to follow-up will not be subject for data imputation.

8. Study Assessments and Procedures

- Study procedures and their timing are summarized in the SoA. Protocol waivers or exemptions are not allowed.
- To minimize questionnaires and procedures for the participants and the study team, we will use 12-month data from the MERINO trial as baseline data in the MERINO:2 study, including person characteristics, patient-reported outcome measures, clinical examination and imaging.
- Adherence to the study design requirements, including those specified in the SoA, is essential and required for study conduct.
- Procedures conducted as part of the participant's routine clinical management and obtained before signing of the ICF may be utilized for research purposes.
- In the event of a significant study-continuity issue (eg, caused by a pandemic), alternate strategies for participant visits, assessments, medication distribution and monitoring may be implemented by the sponsor or the investigator, as per local health authority/ethics requirements.

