The MERINO:2 is an extension of the MERINO trial (EudraCT number 2019-004641-33, Clincaltrials.gov number NCT04579848, REK ID 2020/187524, CTIS number 2023-510523-30-00), with an expanded observational period of 18 months after ending the MERINO trial (i.e. 30 months after staring MERINO). MERINO:2 is an investigator-initiated and open-label observational study. Participants are male and female adults with erosive hand osteoarthritis. Following the completion of the MERINO trial, participants either ended their treatment or were prescribed MTX open-label (oral or s.c. 5-25mg per week as well as folic acid 1mg daily).

Brief Summary:

The primary aim is to demonstrate the superiority of Methotrexate (MTX) over treatment as usual in slowing radiographic progression over 30 months in individuals with erosive hand osteoarthritis (OA).

OA is a leading cause of disability and affecting millions worldwide, with a significant impact on knee, hip, and hand joints. Despite its high prevalence and symptomatic burden, effective disease-modifying treatments remain elusive, with current options limited to pain management and joint replacement.

MTX, recognized for its disease-modifying effects in systemic inflammatory joint diseases, offers promising potential in OA treatment, with previous trials indicating its anti-inflammatory properties and potential for joint damage reduction. In the ongoing MERINO trial, 153 participants are randomly assigned to either MTX or a placebo. Following completion of the trial, several participants have expressed interest in MTX treatment, which is sometimes used off-label for erosive hand OA patients experiencing unmanageable pain and inflammation. As a result, some MERINO trial participants will receive MTX treatment.

In the MERINO:2 study, we will conduct a structured follow-up 18 months post-MERINO trial completion, incorporating hand radiographs and pain questionnaires. This endeavor will furnish invaluable insights into the long-term effects of MTX treatment in erosive hand OA, a gap in current knowledge, particularly regarding structural progression. This will provide valuable data on long-term effects of MTX treatment in erosive hand OA, which is not currently described in the literature, especially on structural progression.

Number of Participants:

We estimate 153 recruited participants from the MERINO trial as potential candidates for the MERINO:2 trial.

Study Arms and Duration:

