All participants recruited to the MERINO trial will be asked to provide conventional radiographs and electronic questionnaires 30 months after starting the MERINO trial. This results in four potential arms of the MERINO:2 trial, depending on the two former arms of the MERINO trial, each with a duration of 12+18=30 months:

- MTX \rightarrow MTX
- MTX \rightarrow Treatment as usual
- Placebo \rightarrow MTX
- Placebo \rightarrow Treatment as usual

Data Monitoring/Other Committee: No

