4.1. Overall Design

The MERINO:2 is an investigator-initiated and open label observational study with one-year parallel group treatment with MTX in male and female adults with erosive hand osteoarthritis.

Eligible participants are those recruited to the MERINO-trial (EudraCT number 2019-004641-33, Clincaltrials.gov number NCT04579848, REK ID 2020/187524, CTIS number 2023-510523-30-00).

After the MERINO trial, participants may either continue treatment as usual or be prescribed MTX open-label (oral or s.c. 5-25mg per week as well as folic acid 1mg daily).

Especially of interest is to compare those who first receive placebo and then treatment as usual throughout the MERINO and MERINO:2 trials with those receiving MTX throughout the whole period, as this comparison will reflect the effect of long-term treatment with MTX over 2,5 consecutive years. Further, the Placebo→MTX crossover group will complement the data from the MERINO trial on shorter MTX treatment.

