8.1.2. OMERACT-OARSI responder criteria

The OMERACT-OARSI responder criteria are validated criteria to assess response to treatment in OA clinical trials (15, 16). The OMERACT–OARSI criteria for response are (1) a relative improvement in AUSCAN pain or physical function \geq 50% and an absolute change \geq 20 mm; or (2) a relative improvement of \geq 20% with an absolute change \geq 10 mm in at least two of the following three categories: AUSCAN pain, AUSCAN physical function, and patient's global assessment. In the OMERACT-OARSI criteria, the AUSCAN pain and function subscale scores are used on a 0-100 scale. Since we used the Likert version of the AUSCAN questionnaire in this trial, the AUSCAN pain and function subscale scores were rescaled from 0-20 and 0-36, respectively, to 0-100. Absolute change was calculated as baseline minus follow-up score, and relative change as absolute change divided by baseline score.

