9.1. Statistical Hypotheses

The primary objective is to demonstrate that MTX is superior to treatment as usual in achieving slower radiographic progression at 30 months. Thus, the null hypothesis to be tested in relation to the primary estimand is as follows:

• Null hypothesis: MTX treatment for 30 months is not different from placebo (12 months) and subsequent treatment as usual (18 months) with respect to the progression of Verbruggen-Veys scoring system in participants with erosive hand OA.

VS.

• Alternative hypothesis: MTX treatment for 30 months is different from placebo (12 months) and subsequent treatment as usual (18 months) with respect to the progression of Verbruggen-Veys scoring system in participants with erosive hand OA.

Secondary outcomes (1):

- Null hypothesis: MTX treatment for 30 months is not different from placebo (12 months) and subsequent treatment as usual (18 months) with respect to the progression of KL scale or OARSI atlas in participants with erosive hand OA.
- Alternative hypothesis: MTX treatment for 30 months is different from placebo (12 months) and subsequent treatment as usual (18 months) with respect to the progression of KL scale or OARSI atlas in participants with erosive hand OA.

Secondary objective (2)

- Null hypothesis: MTX is not different from placebo/treatment as usual with respect to change from baseline to 12/30 months in OMERACT-OARSI responder criteria, AUSCAN or EQ-5D-5L.
- Alternative hypothesis: MTX is different from placebo/treatment as usual with respect to change from baseline to 12/30 months in OMERACT-OARSI responder criteria, AUSCAN or EQ-5D-5L.

Multiplicity control is not relevant for the study.

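### Section 8 makes MERINO month 12 the baseline for imaging and patient-reported outcomes, which conflicts with the 30-month aim and with the secondary hypothesis on change to 12 and 30 months

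*Protocol*

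**What the plan says.** Section 8 states that "we will use 12-month data from the MERINO trial as baseline data in the MERINO:2 study", with the scope "including person characteristics, patient-reported outcome measures, clinical examination and imaging". The reason given is to spare participants and staff extra questionnaires and procedures. No other section names a baseline month for MERINO:2, and none limits this one to descriptive use.

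On patient-reported outcomes, the second secondary hypothesis in Section 9.1 concerns "change from baseline to 12/30 months in OMERACT-OARSI responder criteria, AUSCAN or EQ-5D-5L". Section 8.1.2 defines response as follows: "Absolute change was calculated as baseline minus follow-up score, and relative change as absolute change divided by baseline score". It does not say which month is baseline.

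On the primary endpoint, the Brief Summary in Section 1.1 aims at slower radiographic progression over 30 months, and the four arms are described as "each with a duration of 12+18=30 months". Section 4.1 says of the continuous-MTX versus placebo-then-usual-treatment contrast that "this comparison will reflect the effect of long-term treatment with MTX over 2,5 consecutive years". The primary null hypothesis in Section 9.1 sets 30 months of MTX against 12 months of placebo plus 18 months of usual treatment. Section 1.1 and Table 1 label the endpoint with 18 months. Section 9.3 tests the group difference at study end and writes no change score.

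**The concern.** A month-12 baseline and the hypotheses in Section 9.1 cannot both be followed. For the patient-reported outcomes the clash is explicit. For the OMERACT-OARSI endpoint the baseline is part of the definition, so two analysts following Section 8 and Section 9.1 respectively can report different responder rates from the same data.

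For the radiographs the clash is an inference, because the primary hypothesis states how long treatment lasts and not which film is the reference. The stake is larger, though. Month 12 comes after a year of randomised MTX or placebo. If the month-12 film is subtracted or adjusted for, three things follow:

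- Any difference built up in the only randomised year is removed.
- The change score cannot be computed for an invited participant without a month-12 film. Section 5 invites everyone who entered MERINO, and Section 7.3 rules out imputation for loss to follow-up.
- The 30-month hypothesis is not the one tested.

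**Working it through.** **1. Can the secondary hypothesis be read with a month-12 baseline?**

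- On the MERINO clock, change from month 12 to month 12 is zero for every participant.
- Counted from month 12, the two time points would fall at 12 + 12 = 24 and 12 + 30 = 42 months. The Schedule of Activities (SoA) has neither visit.
- From M00, both time points (M12 and M30) are scheduled visits at which these instruments are collected.

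Only M00 makes the hypothesis coherent.

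**2. Does the baseline change who responds?**

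Criteria from Section 8.1.2: (1) at least 50% and at least 20 points improvement in AUSCAN pain or function; or (2) at least 20% and at least 10 points in at least two of pain, function and patient global assessment. Absolute change = baseline − M30; relative change = absolute change / baseline.

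The scores below are illustrative assumptions: AUSCAN pain on 0–100, with the other two domains unchanged.

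| Case | M00 | M12 | M30 | From M00 | From M12 |
|---|---|---|---|---|---|
| A | 60 | 35 | 30 | 30 points, 30/60 = 50%: responder | 5 points, 5/35 = 14%: non-responder |
| B | 50 | 70 | 35 | 15 points, 15/50 = 30%, one domain only: non-responder | 35 points, 35/70 = 50%: responder |

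The scores are attainable on the 0–20 Likert sum: 12, 7, 6 for A and 10, 14, 7 for B. Reclassification can go in either direction.

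**3. How much of the 30 months does month 12 to month 30 cover?**

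The protocol's own timeline adds up: 12 + 18 = 30 months, and 52 + 78 = 130 weeks. The SoA gives the screening film at week −4 to 0, M12 at week 52 ± 2 and M30 at week 130 ± 10.

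Share = (M30 − M12) / (M30 − reference film), in weeks:

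- Nominal, reference at week 0: (130 − 52)/130 = 78/130 = 60.0%
- Nominal, screening film at week −4: 78/134 = 58.2%
- Lowest: (120 − 54)/(120 + 4) = 66/124 = 53.2%
- Highest: (140 − 50)/(140 − 0) = 90/140 = 64.3%

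So 36% to 47% of the interval, containing the randomised year, is left out. These are shares of time, not of effect. If a fraction f of the 30-month difference is present by month 12, a change from month 12 keeps 1 − f of it: 100%, 60%, 20% or 0% for f = 0, 0.4, 0.8 or 1. The protocol gives no basis for choosing f.

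**4. Does the 18-month label settle the reference film?**

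No. The Overall Design text in Section 1.1 equates 18 months after MERINO with 30 months after its start, and Section 8.2 uses 18 months as a name for the M30 visit. The label fits either reading.

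**The case against.** The best opposing reading is that the Section 8 sentence is operational. It sits among the assessments, its purpose is to avoid a new entry visit, and it never says that change or progression is calculated from month 12. It cannot be applied literally even to person characteristics, since the SoA collects demographics and medical history at M00 only. An SoA footnote uses baseline for the start of MERINO when it describes height measurement. Read with Section 9.1, M00 is then the natural baseline, and the reference film and covariates are matters for the SAP. Month 12 also has a legitimate use for the placebo-to-MTX group, which Section 4.1 wants to study.

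Parts of this stand. Nothing in the protocol states that radiographic progression is measured from month 12, so the consequence for the primary endpoint is conditional. The responder cases are constructed, and the 53% to 64% describes calendar time only.

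The rest does not remove the problem. The protocol never says that the month-12 baseline is only administrative, and it names imaging and patient-reported outcomes without limit. The footnote shows the word being used in two senses, which is a further reason to define it. A SAP cannot resolve this by adding detail, because it must follow one section and depart from the other.

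**Conclusion.** The concern holds. For OMERACT-OARSI response, AUSCAN and EQ-5D-5L, Sections 8 and 9.1 set incompatible baselines. Following Section 8 as written makes the change to month 12 zero and alters the responder definition. For the primary endpoint, a month-12 reference would turn a stated 30-month comparison into one covering nominally 60% of the period (53% to 64% within the visit windows) and would discard the randomised year. That part depends on month 12 being subtracted or adjusted for, which Section 8 suggests but no section states.

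The windows and response criteria are the protocol's; the AUSCAN scores are assumed. The number of participants reclassified and the effect on power cannot be derived, because Section 9.5 gives no statistical basis for the sample size and no effect size or standard deviation is stated. The point must be settled before outcomes are analysed, because it determines what a named secondary endpoint measures and leaves the primary endpoint's reference in doubt.

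**What to change.** - In Sections 1.1, 3, 8 and 9.1, name the MERINO screening radiograph and the M00 questionnaires as the reference for the 30-month hypotheses.
- In Section 8.1.2, state that baseline in the OMERACT-OARSI formula is M00.
- Replace the 18-month label by month 30 wherever it denotes the M30 visit (Sections 1.1, 3, 6.5, 6.9, 7.3, 8.1 and 8.2).
- Restrict the month-12 baseline sentence in Section 8 to a separately labelled analysis of the period after MERINO. This keeps the placebo-to-MTX question.

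The cost is one protocol amendment with ethics approval (Section 10.1.1) and matching SAP wording. No new data collection is needed, since the SoA already schedules the screening films and M00 questionnaires, although their completeness is not shown. The change aligns baseline and hypothesis only. The 30-month contrast stays open to confounding, because treatment after month 12 is chosen by physician and participant (Section 6.3).

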8.1. Patient-reported outcome measures

The following patient-reported questionnaires are to be answered at 18 months using ViedocMe. See Appendix 2 for language and wording of the questionnaires.

8.1.1. VAS pain

The time interval in which pain should be assessed varies across studies. A long interval may lead to recall bias, whereas a too short interval may possibly not adequately cover the whole pain spectrum. In the current study, we ask the participants about their symptoms the last 48 hours:

- Overall finger joint pain, VAS 0-100
- Overall thumb base joint pain, VAS 0-100
- Pain in most painful finger joint ("index joint") VAS 0-100; in case of two or more equally painful joints, a joint is selected randomly
- Overall disease activity in hands, VAS 0-100
- Overall pain in all body joints, VAS 0-100

8.1.2. OMERACT-OARSI responder criteria

The OMERACT-OARSI responder criteria are validated criteria to assess response to treatment in OA clinical trials (15, 16). The OMERACT–OARSI criteria for response are (1) a relative improvement in AUSCAN pain or physical function \geq 50% and an absolute change \geq 20 mm; or (2) a relative improvement of \geq 20% with an absolute change \geq 10 mm in at least two of the following three categories: AUSCAN pain, AUSCAN physical function, and patient's global assessment. In the OMERACT-OARSI criteria, the AUSCAN pain and function subscale scores are used on a 0-100 scale. Since we used the Likert version of the AUSCAN questionnaire in this trial, the AUSCAN pain and function subscale scores were rescaled from 0-20 and 0-36, respectively, to 0-100. Absolute change was calculated as baseline minus follow-up score, and relative change as absolute change divided by baseline score.

8.1.3. Australian/Canadian Hand Index (AUSCAN)

The AUSCAN pain subscale

The hand OA-specific questionnaire AUSCAN includes five items about pain at rest and during activities (gripping, lifting, turning and squeezing objects) during the last 48 hours (17). In the MERINO trial we are using the Likert version, but AUSCAN also exists as numeric rating scales (NRS) and VAS. The response categories for all items are ranging from 0 ("None") to 4 ("Extreme"). A sum score (0-20 scale) can be calculated. There are no instructions on how to handle missing values, and the "half-rule" are applied in the MERINO trial, which means that missing items should be replaced with the mean of the answered items if 50% or more of the items in the respective subscale have been answered. The scale has been translated to Norwegian and validated (18).

The AUSCAN physical function subscale

The hand OA-specific questionnaire AUSCAN includes nine questions concerning tasks requiring grip strength and precision tasks (17). The response categories for all items are ranging from 0 ("None") to 4 ("Extreme"). A sum score (0-36 scale) can be calculated. There are no instructions on how to handle missing values, and the "half-rule" are applied in the MERINO trial. The scale has been translated to Norwegian and validated (18).

The AUSCAN stiffness subscale

The hand OA-specific questionnaire AUSCAN includes one question concerning stiffness in the hands in the morning with response options ranging from 0=none to 4=extreme (17). The scale has been translated to Norwegian and validated (18).

8.1.4. The EuroQol 5 dimensions 5 levels (EQ-5D-5L)

The generic instrument EQ-5D-5L captures five health dimensions (mobility, self-care, usual activity, pain/discomfort and anxiety/depression) (19). The EQ-5D-5L encompasses 243 different health states and is one of the most widely used utility instruments in the field of medicine (20). The questionnaire has been translated to Norwegian, and has been used in several Norwegian studies (21). We used the five-level version (EQ-5D-5L). On the EQ-VAS the participant was instructed to self-rate their health on a 0-100 VAS, where 0=worst health and 100=best health. The EQ-5D-5L can be converted to a single summary index by using a formula with different weights to each level in the dimension. European value sets have been defined (22). Based on participant responses, an index score will be calculated to reflect the participant's HRQoL, using the preference scores published from a UK population (23).

8.2. Conventional hand radiographs

The participants are invited for bilateral hand radiographs at 18 months.

The participant is sitting with the hand on the detector (posteroanterior view), and front images are obtained (source to image-receptor distance (SID): 115 cm; exposure: 46 kVp and 2 mAs).

OA in the DIP, PIP, MCP, first carpometacarpal (CMC-1) and scapho-trapezio-trapzoidal (STT) joint will be assessed according to validated scoring systems:

- *The Kellgren-Lawrence (KL) scale* from 1957 is a global index that grades OA on a semiquantitative five-point scale based on the presence/severity of osteophytes/ossicles, narrowing of the joint space, sclerosis of the subchondral bone, pseudocystic areas, and altered shape of bone ends (24, 25). We will use a modified version, as previously used in the Framingham study (26). The original publication includes DIP, PIP, thumb IP, MCP and CMC-1, and the STT joint will be added in the MERINO trial.
- *The Verbruggen-Veys scoring system* has been proposed for the evaluation of the anatomical phases in patients with erosive disease (N=normal, S=stationary, J=joint space narrowing, E=erosive, R=remodelled) (27). In the original publication, DIP, PIP, thumb IP and MCP (2-5) joints were included. In the MERINO trial, only the 2nd-5th DIP and PIP joints will be assessed. Joints with remodelling in more than 70% of the joint will be scored as E/R, whereas completely remodelled joints will be scored as R.
- Using the *OARSI atlas* from 1995 (revision from 2007) (28, 29) as a reference, the presence/severity of individual features such as osteophytes (grade 0-3) and joint space narrowing (grade 0-3), will be assessed on semi-quantitative scales. In the OARSI atlas only DIP, PIP, thumb IP and CMC-1 are included. In the MERINO trial, also the MCP and STT joints will be scored.

8.3. Safety Assessments

All participants will be monitored according to the National procedure for diagnosis, treatment and follow-up of rheumatoid arthritis in Norway (30), chapter 10.1. Blood tests recommended for monitoring: Hemoglobin, red blood cells, white blood cells with diff. Counts, platelets, ALT, creatinine, (SR and CRP). Patients with comorbidity, abnormal blood tests, and / or polypharmacy treated with DMARD may require more frequent laboratory tests than the general recommendations in the table.

| Drug | Monitoring interval based on duration of treatment | | |
|-------------|--|------------|-----------|
| | <3 months | 3-6 months | >6 months |
| Metotreksat | 2–4 weeks | 8–12 weeks | 12 weeks |

Table: Monitoring interval for blood testing in patients using DMARDs

8.3.1. Side effects and abnormal laboratory results

Discontinuation of study intervention is required by the investigator when a participant meets one of the conditions outlined in the algorithm below or if the investigator believes that it is in best interest of the participant.

The algorithm below provides recommended actions in case of side effects and abnormal laboratory results according to the shared care protocol by Oxford University Hospital, NHS (https://www.ouh.nhs.uk/oxparc/professionals/documents/methotrexate-scp-july-2015.pdf). In the event of a medically significant unexplained abnormal laboratory test value the test should be followed up until they have returned to the normal range and/or an adequate explanation of the abnormality is found.

| Side effects | Action |
|---|---|
| WBC < 4 x 109/I WBC < 3.5 x 109/I | Adults: Perform a differential and increase frequency of monitoring. Withhold and discuss with specialist. Bone marrow suppression can occur abruptly. |
| Neutrophils < 2 x 109/I | Withhold and discuss with specialist. Bone marrow suppression can occur abruptly. |
| Platelets < 150 x 109/l | Withhold and discuss with specialist. Bone marrow suppression can occur abruptly. |
| MCV >110 fl MCV >105 - 110 fl | Stop methotrexate and seek advice. Check folate, B12 and thyroid function tests and treat if appropriate. If WBC normal repeat in 4 weeks. |
| Liver function 2 - 3 fold rise in ALT >3 fold rise in ALT | Reduce the dose and repeat in 1 - 2 weeks. Withhold until discussed with specialist. |
| Renal impairment | Patients who develop dehydration, pre-renal or acute renal failure while on methotrexate should have methotrexate withheld and FBC monitored closely. Review any changes in medication particularly ACEI and ARB. |
| Unexplained fall in albumin | Withhold and speak to specialist. |
| Nausea and/or vomiting | Usually improves over time. If troublesome for adults consider: Increasing the dose of folic acid to 5 mg daily up to 6 days a week - omitting on the day methotrexate is taken. Splitting methotrexate dose over one evening and next morning. A short-term anti-emetic. |
| | If unable to tolerate refer back to specialist for review. |
| Hair loss | Usually mild, rarely significant. Reversible on stopping drug. |
| Rash | Withhold treatment and discuss with specialist. |

| Mouth ulcers, mucositis | Mouth ulcers may respond to increasing folic acid as above. If severe despite extra folic acid stop methotrexate and refer to a specialist for advice. |
|---|--|
| Menstrual dysfunction/amenorrhoea | May occur during treatment and for a short while after cessation. |
| Otherwise unexplained dyspnoea or cough (especially if accompanied by fever/sweats) | Methotrexate pneumonitis may occur. Withhold treatment, arrange chest X-ray and discuss urgently with consultant. |
| Abnormal bruising | Withhold until FBC result available. |
| Sore throat or other unusual infection | Urgent FBC and withhold until FBC result available. Susceptible to opportunistic infections such as viral wart, tuberculosis and pneumocystitis. |
| Cervical dysplasia | Contact gynecologist. |
| Diarrhea | Consider reducing dose. |
| Fever, chills | Withhold until FBC result available |

FBC=full blood count, MCV=mean corpuscular volume, WBC=white blood cells, ALT= alanine aminotransferase

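### Section 8.3.1 requires methotrexate to be discontinued for any condition in its table, but 8 of the 21 listed conditions carry no stop or withhold action

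*Protocol*

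**What the plan says.** Protocol section 8.3.1 begins: "Discontinuation of study intervention is required by the investigator when a participant meets one of the conditions outlined in the algorithm below". The same sentence adds a second ground, the investigator's judgement of the participant's best interest. The trigger is meeting a listed condition. It is not limited to conditions whose listed action is to stop.

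The next paragraph describes the same table differently: "The algorithm below provides recommended actions in case of side effects and abnormal laboratory results". The actions then vary by condition:

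- WBC <4: "Perform a differential and increase frequency of monitoring". Withholding is tied to the lower threshold, <3.5.
- MCV >105-110: "Check folate, B12 and thyroid function tests and treat if appropriate. If WBC normal repeat in 4 weeks". Stopping is tied to MCV >110.
- ALT 2-3 fold rise: "Reduce the dose and repeat in 1 - 2 weeks". Above 3 fold: "Withhold until discussed with specialist".
- Nausea and/or vomiting: options include more folic acid, a short-term anti-emetic, and "Splitting methotrexate dose over one evening and next morning".
- Diarrhea: a dose reduction is to be considered.
- Hair loss: "Usually mild, rarely significant. Reversible on stopping drug".

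Elsewhere, section 6.1.1 lets the physician depart from the standard dose, for example because of adverse events, and section 6.6 lets the treating physician choose other doses. Section 8 rules out protocol waivers and exemptions.

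**The concern.** The opening sentence is a safety rule in mandatory terms, and for several conditions it prescribes a different action from the table that it introduces. A physician who sees a 2-3 fold ALT rise is told by the sentence to discontinue MTX and by the table to lower the dose and retest. Both cannot be done.

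These are not remote situations. Section 2.3.1 has patients advised to report vomiting, diarrhea and mouth ulcers, among other symptoms. Two physicians who read 8.3.1 in good faith could handle the same report differently, one ending treatment and the other adjusting it. Section 8.4 also attaches follow-up duties to adverse events that caused discontinuation, so the choice carries through to the safety records.

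**Working it through.** The protocol states no figure on this point, so the check is a tally of the table in 8.3.1 against its opening sentence.

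**Size of the table.** There are 10 rows from WBC to rash and 8 from mouth ulcers to fever/chills: 10 + 8 = 18 rows. Three rows (WBC, MCV, liver function) hold two thresholds each, so there are 18 + 3 = 21 conditions.

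**Classification by the action given.**

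| Action on MTX | Conditions | Count |
|---|---|---|
| Reduced or split MTX dose, expressly | ALT 2-3 fold; nausea/vomiting; diarrhea | 3 |
| Monitoring or tests only, beside a stop or withhold threshold | WBC <4; MCV >105-110 | 2 |
| No MTX instruction | hair loss; menstrual dysfunction; cervical dysplasia | 3 |
| Stop only if severe despite extra folic acid | mouth ulcers | 1 |
| Withhold | WBC <3.5; neutrophils; platelets; ALT >3 fold; renal impairment; albumin; rash; dyspnoea/cough; bruising; sore throat; fever | 11 |
| Stop outright | MCV >110 | 1 |

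The total is 3 + 2 + 3 + 1 + 11 + 1 = 21.

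**No stop or withhold action.** 3 + 2 + 3 = 8 of 21 conditions. If the three two-threshold rows are left whole, each contains a stop or withhold action and drops out, leaving nausea/vomiting, diarrhea, hair loss, menstrual dysfunction and cervical dysplasia: 5 of 18 rows.

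**Sensitivity to judgement.**

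- The narrowest count of direct contradictions is 3, the conditions whose action itself speaks of MTX dosing.
- For WBC <4 and MCV >105-110, continued MTX is inferred from the contrast with the neighbouring threshold. Adding them gives 3 + 2 = 5.
- Mouth ulcers are outside the 8 because the row does contain a stop. Its first step, extra folic acid, arguably also assumes continued treatment. Adding it gives 6 that presuppose continuation, and 8 + 1 = 9 with no unconditional stop or withhold.

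**Sensitivity to the flattened table.** In the three split rows, the match of threshold to action is read from the order of the extracted cells. Each row holds one milder action and one stop or withhold action, so swapping the pairing leaves the count at 8. Nausea/vomiting and diarrhea are single-condition rows and show the conflict without any pairing.

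**Does other text resolve it?** Sections 6.1.1 and 6.6 allow dose changes, which fits the table but does not remove the mandatory wording of 8.3.1. The best-interest clause adds a ground for stopping and gives no permission to continue. These counts are of table entries and say nothing about how many participants would be affected.

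**The case against.** The strongest reply is that nobody would read the sentence literally. The following paragraph calls the entries recommended actions, the table is laid out by action, and sections 4.3, 6.1.1, 6.3 and 6.6 leave dose and continuation to the treating physician, who has the row in front of them. Following each row is very probably what was meant. That bears on how serious the slip is, but it does not make the sentence right: the trigger as written is meeting a condition, and section 8 allows no waivers.

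A second reply is that a firm statement that eight conditions contradict the rule, or even that five presuppose continued MTX, goes too far. This stands in part. Only three conditions speak of MTX dosing, two more rest on inference, and three give no instruction and so do not oppose stopping. The direct conflict should be rested on the three.

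A reader might also infer that the 11 withhold entries contradict the rule, on the view that discontinuation means permanent discontinuation. Then only 1 of 21 conditions would match outright, or 2 with severe mouth ulcers. The protocol does not support this. Section 8.3.1 does not say permanent. Section 7.1, which does, only refers to section 8.3 for safety assessments and does not make the table a list of criteria for permanent stopping. Withholding can fairly be read as a temporary discontinuation, and those entries then agree with the opening sentence.

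**Conclusion.** The opening sentence of 8.3.1 is wrong as written. It requires discontinuation for every listed condition, while 8 of 21 conditions (5 of 18 rows unsplit) carry no stop or withhold action, and 3 of those 8 expressly direct continued MTX at a reduced or split dose. The count of 8 rests on treating withhold as a form of discontinuation and on leaving mouth ulcers out because of its conditional stop.

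The consequence is limited. Read literally, the sentence errs toward stopping, so the risk is needless discontinuation and inconsistent handling. A reader might infer a danger to participants or a bias in the MTX comparison, but the document supports neither. No row with a stop or withhold action is weakened by the sentence. Participants who stop are still invited to follow-up under section 7.2, and nothing in the protocol shows how often these conditions would arise. It should be corrected because it is a safety rule with two meanings.

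**What to change.** Replace the opening sentence of section 8.3.1 with:

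> MTX must be stopped or withheld where the action column below says so; for all other conditions the listed action is followed and MTX may continue. The investigator may also discontinue MTX whenever this is in the participant's best interest.

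The table stays as it is. A general definition of every withhold as a temporary interruption should not be added. The renal impairment row names no test or advice that would end the interruption, and for suspected methotrexate pneumonitis, which section 2.3.1 says can be fatal, the protocol does not say that MTX is expected to resume.

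The cost is the replacement of one sentence at the next amendment, with no new visits, tests or data.
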